6.0 Data Analysis and Statistical Considerations

Quantitative Analysis: All survey and interview data will be presented using basic descriptive statistics such as the frequency, % and mean (SD). To compare the intervention effect (screening rate, awareness, etc) within same participants before and after the intervention, Mixed-effects logistic regression model will be utilized. The mixed-effect model will also account for multilevel clusters such as households and districts. The between-subject effects to compare the impact of different regions with and without intervention implemented treating them as intervention and control group will be tested using Chi-squared test for single level samples and mixed-effects logistic for multilevel data. Outcome related factors such as demographic information and other barriers will be measured using descriptive statistics and to test the intervention effect by using multiple regression models.

Qualitative Analysis: For the qualitative data gathered for **aims 1 and 2**, we will use an iterative analysis approach based upon grounded theory⁷⁰ using Dedoose. We will transcribe recorded interviews and field notes into French and English (languages of the research team) and enter both into Dedoose. We will conduct the grounded theory analytic methods in steps.⁷²⁻⁷⁵ **Step 1: Initial Review of the Data.** We will divide the entire data set among research team members and identify initial overarching concepts. We will develop the coding scheme as we label, define, and group concepts into categories corresponding to the initial conceptual framework. We will track demographic, contextual, and experiential items that are important to understanding 1) how age or gender impacts the opinion of cervical cancer screening eligible women or their contacts or 2) how perceptions of the educational curriculum may differ between trainer and trainee. **Step 2: Developing a Coding Scheme.** Next, we will develop a codebook consisting of the labels, definitions, and illustrations of categories formulated in Step 1. We will circulate the codebook for review by the entire team, which we will then pilot and revise by using selections of text from the data. When it is clear that the coding scheme is appropriate, two coders each from UIC and Senegal/UCAD will be trained to use it. We will repeatedly code the same sections of text and compare the results, discussing and resolving disagreements, until we reach a level of .80 agreement. **Step 3: Coding.** We will code the data using the coding scheme by first reviewing the interview transcripts and field notes and assigning sections of text to the corresponding coding categories. All staff at the UIC and Senegal/UCAD sites will code all data to lay the groundwork for analysis and reporting. We will also code for missing data patterns. **Step 4: Pattern Coding.** We will examine the relationship within and between codes in order to identify overarching themes and patterns of variation. We will continue pattern coding until saturation, when no new quotations appear.⁷⁴ **Step 5: Memoing.** At each of the aforementioned steps we will write short, descriptive statements to a) document ideas during preliminary data review, b) define codes during coding, c) concisely describe items not coded, and d) describe the outcomes of specific Atlas/ti 7 queries. We will then scan memos and sort them to form clusters, categories, and causal networks.⁷²

Mixed methods Analysis and Writing. Mixed methods involves integrating the multiple types of data using well-accepted designs including: triangulation, explanation, transformation, and exploration.⁷⁵ We will use both SAS and Atlas/ti to further analyze data that will have already been collected, coded, and analyzed. Key to this integrated analysis is looking for intersections across levels that may explain: **1)** Which access facilitators best address barriers to seeking cervical cancer screening services among women who are most at risk? **2)** What benefits do interventions at each level of intervention (individual, household, or community) provide? **3)** What role does gender or age play in affecting barriers to accessing screening? **4)** What are the most influential sources that change motivation of screening eligible women change over time? **5)** What will most likely predict

that screening eligible women recommend screening to their peers? The analyzed data will be used to generate mixed methods publications responding to these key themes and will add to the body of knowledge for improving initial uptake and sustained utilization of cervical cancer screening services.

Power calculations

Clusters and Population: There will be three clusters comprising separate districts (Kedougou, Salemata, and Saraya) in Kedougou. Using two independent proportion method of cluster randomization power analysis (PASS13), to obtain the power 80% under significance level 0.05, the 10% difference of the screening rate with assumed ICC 0.01 requires n=15 per each of 3 clusters. Tables 2, 3, and 4 outline the data collection methodology for each aim. These data will be collected within each cluster at baseline and every six months - coinciding with a crossover of a new (random) cluster. Our selected sites are comprised of zones representative of region including rural, district center, semi-urban, and urban. Contamination is unlikely given distance (the distance between sites ranges from 32 kilometers / 45 minutes by car to 3 ½ hours by car).

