AIM 3	How does a peer education program impact the cervical cancer screening service initial uptake by eligible women seeking a first-time screening and ensure sustained utilization and continuing impact of the cervical cancer screening service?

Study Design: Figure 2 is a schematic example for this trial design. In this example, Cluster 1 (randomly selected) crosses to the intervention arm at Period 2, Cluster 2 (randomly selected) crosses over to the intervention arm at Period 3, and so on. By the end of the study, all clusters will cross over to the intervention arm (one-way), though in random order. At the end of the final time period, the outcome of interest is compared between the intervention and control periods within each cluster. Differences in service utilization and recommendation will be compared, whereby clusters serve as their own controls as they cross over from the control to intervention group.

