To achieve Aim 1, we will orient 3 CGs in each cluster. Through a participatory process involving CG leaders, health service leaders, midwives, and community members (women and men) we will develop, field test, and refine quantitative individual-level surveys that gather access barriers data corresponding to the variables listed in Table 2. We will conduct quantitative **a) Individual Baseline Surveys** with the same enrolled women (up to 25) and the same 10 men in each site per cluster. These data will be collected at baseline and at the end of the study period (after 3 years). We will also conduct **b) Individual Interval Interviews** with the same women (up to 25) and the same 10 men in each site per cluster. These data will be collected at baseline and every six months through the end of the study period (after 3 years). Therefore, these data will be collected six (6) times. These pre-tested, approved standard individual-level questionnaires (close ended) will be administered (face-to-face) by an RA of the same gender as the participant in the participants' preferred language (Malinke, Pulaar, or French). We will also conduct **c) Women's Focus Groups**. Through these FGs we will collect qualitative data, from women stratified by age, describing demand-side access barriers and facilitators (Table 2). The Research Assistant will moderate the 45 minute FGs in the preferred language (Malinke, Pulaar, or French) and two PCVs will observe and record written observations in real time. We will audio record the sessions (to be transcribed into both French and English). The Research Assistant and PCVs will review the audio record and confirm all notes. Below are described the recruitment and enrollment procedures for these data collection events.

Recruitment and Enrollment of Participants Followed within Households

We will utilize a random cluster sampling method to select ten (10) households in each of the three (3) sites per cluster. We will convenience sample one woman and one man in each of the households among those

who express a willingness to participate. We will ensure that the ten (10) chosen households fall within the households where the educational Care Group intervention takes place. Given that each Care Group will cover between 80 and 100 households, we are expecting to enroll participants from 10% of the households where the Care Group intervention occurs.

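### The before/after contrast in this one-way stepped wedge names no calendar-period term, so any background rise in screening would be counted as intervention effect

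*Protocol*

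**What the plan says.** The Study Design text in section 3.0 describes a stepped wedge over three clusters, one per district: "By the end of the study, all clusters will cross over to the intervention arm (one-way), though in random order". The effect is read inside each cluster: "the outcome of interest is compared between the intervention and control periods within each cluster", "whereby clusters serve as their own controls as they cross over from the control to intervention group".

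Section 6.0, Quantitative Analysis, makes this the effect analysis: "To compare the intervention effect (screening rate, awareness, etc) within same participants before and after the intervention, Mixed-effects logistic regression model will be utilized". On adjustment it says: "The mixed-effect model will also account for multilevel clusters such as households and districts". It also plans a second, separate comparison: "The between-subject effects to compare the impact of different regions with and without intervention implemented treating them as intervention and control group", to be tested by chi-squared or mixed-effects logistic regression. It does not say that this comparison is made within the same data collection round.

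On the number of rounds, the Aim 1 procedures say "Therefore, these data will be collected six (6) times". The power calculation states that "the 10% difference of the screening rate with assumed ICC 0.01 requires n=15 per each of 3 clusters", and that one new cluster crosses at each six-month round. Neither the design text, the analysis text nor the power calculation mentions period, calendar time or secular trend.

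**The concern.** In a one-way design, intervention status is tied to calendar time: later rounds are the treated rounds. A contrast of after with before in the same clusters or people therefore measures the intervention plus whatever else changed over those months. The randomised step order is there to separate the two, by comparing crossed and not-yet-crossed clusters in the same round. The before/after model does not use it.

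Aim 3 asks whether peer education raised screening. If screening drifts up for another reason, this contrast can give a positive answer with no intervention effect. The protocol documents no drift, but it describes possible sources:

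- a service rolled out across the region only between 2010 and 2013 (Preliminary Work in Kedougou);
- general health education by all Care Groups from the start, including control periods (section 3.0, Aim 2);
- repeated six-monthly interviews of the same people about screening (section 3.0, Aim 1);
- screening locations given to participants who ask (section 5.0, Participant Referrals).

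**Working it through.** **The plan's own figure.** The only nearby figure is n=15 per cluster for 80% power. Read as three clusters of 15 per arm with design effect 1 + 14 × 0.01 = 1.14, two-sided power is 31% for 5% vs 15% and at most 53% (0% vs 10%). It is not reproduced on that reading. This is a separate matter, and the argument below does not depend on it.

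**Inputs.** Three clusters, one crossing per six-month round, so at rounds 2, 3 and 4 (section 6.0, Power calculations). Six rounds are stated. Baseline plus every six months to three years would give seven, and four is the fewest that lets all three clusters cross. Women interviewed per cluster: 45 (Table 2, interval interview) to 75 (up to 25 at each of three sites, Aim 1 text). Assumed: a 5% starting rate, which is the 2014 campaign figure in section 1.0, and the background rise.

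**Gap in time, six rounds.** Mean intervention round minus mean control round:

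- Cluster 1: 4.0 − 1.0 = 3.0
- Cluster 2: 4.5 − 1.5 = 3.0
- Cluster 3: 5.0 − 2.0 = 3.0

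In general the gap is T/2 for T rounds: 2.0 at four, 3.5 at seven. With no true effect and a linear rise of g points per step, the before/after estimate is T/2 × g. At six rounds, rises of 1, 2 and 3 points per step give false effects of 3, 6 and 9 points, against the planned 10. With period effects the false effect is 0.

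**Between-region comparison.** Only rounds 2 and 3 contain both conditions. Pooled over all six rounds, the mean control round is 10/6 = 1.67 and the mean intervention round is 53/12 = 4.42, a gap of 2.75 steps. Pooling therefore gives little protection; comparing within a round removes a common trend.

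**False positives (illustrative).** Zero effect, six rounds, participant intercept SD 0.8, district fixed effects in the before/after models, no district-by-period variance, 400 runs, 45–75 women per cluster, simulation error at most about 5 points either way. The assumed three-year slopes are 5/6 = 0.83 and 10/6 = 1.67 points per step.

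| Model | 5%-to-10% slope | 5%-to-15% slope |
|---|---|---|
| Spurious effect, before/after (3 × step) | 2.5 points | 5 points |
| Before/after, no period term | 27–36% (OR 1.5–1.6) | 71–87% (OR about 2.0) |
| Between-region, pooled over rounds | 26–35% | 67–83% |

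With no drift, the before/after model rejects in 5%. Under drift, the before/after model with period effects rejects in 4–6% (OR about 1.0), and the between-region model restricted to rounds 2 and 3 with a round effect rejects in 5–6%. At seven rounds, the before/after model without period rejects in 36–54% and 81–97%. A second, simpler simulation (independent outcomes, 75 women, 500 runs) gave 44%, 95% and 100% at rises of 1, 2 and 3 points per round, and 4.4–5.0% with period effects.

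**Cost in precision.** The residual sum of squares of the intervention indicator at six rounds is 5/6 + 8/6 + 9/6 = 3.67 after district, and 4 − 1/3 − 8/3 = 1.0 after district and period. The variance ratio is 3.67 (3.0 at four rounds, 3.8 at seven). With residual variance (0.05 × 0.95 + 0.15 × 0.85)/2 = 0.0875, m women per cluster and independent rounds:

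- SE = √(0.0875 / (m × RSS)).
- m = 45: 95% half-width goes from 4.5 to 8.6 points.
- Power for 5% vs 15%: at m = 15, 0.71 falls to 0.26. With period effects it is 0.62 at m = 45 and 0.83 at m = 75.
- With within-person correlation 0.1: 0.75 falls to 0.28 at m = 15, then 0.67 and 0.87.

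**The case against.** The strongest reply is that covariates belong in a statistical analysis plan, which was not available here, and that the list of what the model accounts for is open-ended. A mixed-effects logistic model does not exclude period effects. If the protocol were merely silent, that would settle it. But it states a contrast, before against after and control against intervention periods within cluster, and that contrast is confounded with time when followed as written.

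The between-region comparison can fairly be read as comparing regions of different status at the same time, and on that reading it is sound (5–6% false positives). It remains a separate test, is not said to be within round, and does not correct the before/after estimate. Section 6.0 also mentions multiple regression for demographic factors and barriers; time is not among the factors named.

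The size of the bias is open to challenge. Section 3.0 ties initial uptake to the first six months. Comparing only the rounds either side of crossover has a gap of about one step, so the two assumed slopes give 0.83 and 1.67 points rather than 2.5 and 5. The Study Design text, however, compares intervention with control periods without that restriction. The simulated outcome can recur each round, whereas a first screening happens once, and household and district-by-period variation are left out. Low use in 2014, after the rollout, is also weak evidence for an upward trend. These points stand: the rejection rates are illustrations, and the figures for the period-adjusted model are a best case. The direction of the bias under a rise is not affected.

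**Conclusion.** The concern holds. As written, the effect analysis cannot tell the intervention from a change over time, and at six rounds it turns a rise of g points per step into an apparent effect of about 3g. That multiple follows from the stated design and averaging over all rounds. The value of g does not come from the protocol, so the spurious effects and false-positive rates are conditional on the assumed slopes; with no drift the before/after model behaves correctly. Because this is the stated analysis for the Aim 3 impact question, it should be corrected before analysis.

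**What to change.** State one effect model in section 6.0: mixed-effects logistic regression with an intervention indicator, a fixed effect for each six-month period, district as a fixed effect (three districts are too few to estimate a variance well), and a participant random effect, keeping the household level already named. For initial uptake, count first screenings in each period among women not yet screened. Say that any between-region comparison is made within the same round. Label simple before/after and chi-squared results as descriptive, and align the Study Design text in section 3.0.

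No new data are required. The price is precision, as calculated above, so the power statement must be redone for this model with its base rate, number of rounds and women per cluster stated. One limit remains: with three districts, a trend specific to one district still cannot be separated from the effect, and the protocol should say so.

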Overview of Study Data Collection: To achieve all aims, we will conduct a cluster-randomized stepped wedge study across three representative clusters (each containing a district center and two rural sites) in the Kedougou region. For each aim we will collect data at baseline and at 6-month intervals in each cluster (data collection intervals coincide with the initiation of the intervention in a new cluster). In aim 1, we will develop (through a participatory approach), pilot, and conduct surveys and interviews of eligible clients as well as focus groups (FG) (women ages 30-44 and 45-59) and interviews of men (ages 30-59). For aim 2, we will describe the development, piloting, implementation, and adaptation of an aim 1-informed context-specific multi-level peer education curriculum across clusters through the stepped wedge approach^{59,60} in the Kedougou region. We will collect quantitative program reach data and qualitative process evaluation data at each time period. These data will be used to adapt the intervention over time. To achieve aim 3, we will collect aggregated health service level utilization data and individual surveys.

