5.0 Sources of Material, Protection Against Risks and Informed Consent

Sources of Material.

Sources of research material will include: 1) **Individual Baseline surveys** of adults (21 and above) in households with screening eligible women, 2) **Individual Interval Semi-structured Interviews**: semi-structured interviews with target age women eligible for screening and receiving cervical cancer prevention services or men living in a household with target age eligible women, 3) **Focus Groups** with women or Care Group Volunteers, and 4) **Document Review**: de-identified, aggregated health service or care group data,

Individual Baseline surveys

The baseline survey will gather information through adults (age 30 to 59) willing and able to provide the requested information. Once surveyed, individuals from the same households will be followed over time and re-surveyed at each data collection period. The pre-tested standard individual baseline surveys (close ended) will be administered (face-to-face) in the participants' preferred language (Malinke, Pulaar, or French). These will be administered by a Senegalese Research Assistant with assistance by PCV research assistants. This data collection will occur at baseline and at the end of the data collection period. Peace Corps Volunteers will assist the PI and Co-I's in ensuring the fidelity of this data collection.

Individual Interval Semi-structured Interviews

All screening-eligible women and all men aged 30 to 59 in all selected households will be interviewed. The pre-tested standard individual-level questionnaires (semi-structured) will be administered (face-to-face) in the participants' preferred language (Malinke, Pulaar, or French). These will be administered by a Senegalese Research Assistant with assistance by PCV research assistants. Aim 1 (access determinants, cervical cancer risk), Aim 2 (screening recommendation), and Aim 3 (screening uptake / utilization) data will be collected through this interview. All sites will be monitored for consistent and accurate collection of this data. The data collection instrument will be employed at baseline and every 6 months during the data collection period. Peace Corps Volunteers will assist the PI and Co-I's in ensuring the fidelity of this data collection.

Focus Groups

Aim 1 Focus Groups:

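### The between-district comparison has no stated baseline anchor, so with three districts their chance starting differences enter the estimated effect

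*Protocol*

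**What the plan says.** The Quantitative Analysis paragraph of protocol section 6.0 sets out two main analyses of the intervention effect.

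- The first is a before/after comparison: "within same participants before and after the intervention, Mixed-effects logistic regression model will be utilized". The next sentence adds: "The mixed-effect model will also account for multilevel clusters such as households and districts".
- The second sets districts side by side: "The between-subject effects to compare the impact of different regions with and without intervention implemented treating them as intervention and control group". These effects "will be tested using Chi-squared test for single level samples and mixed-effects logistic for multilevel data".

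A last sentence plans "to test the intervention effect by using multiple regression models", with demographic data and other barriers as the factors. The baseline value of the outcome is not among them.

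The study design text in section 3.0 gives a different basis for the comparison: "clusters serve as their own controls as they cross over from the control to intervention group". The baseline that this needs is collected. Section 2.0 says: "For each aim we will collect data at baseline and at 6-month intervals in each cluster". Section 5.0 repeats it for the individual interviews and for the facility uptake records: "The data collection instrument will be employed at baseline and every 6 months during the data collection period". The power paragraph of section 6.0 names three clusters, which are separate districts, an ICC of 0.01 and a 10-point difference in screening rate.

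**The concern.** The between-district comparison is the only stated contrast that compares intervention with control at the same calendar time, so a reader would lean on it to rule out a time trend. Written as a two-group comparison, it measures the difference in level between districts. Three districts in random order need not start at the same level, and section 6.0 says the sites range from rural to urban. If the district that crosses first starts higher or lower than the others, that gap is counted as part of the effect. The data that would remove it are already being collected.

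A district random effect does not settle this within a single round. One district against two gives no way to tell a difference between districts from the intervention. The separation has to come from each district's own earlier rounds.

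**Working it through.** **The plan's own figure.** The plan gives no figure for the size of starting differences. Its only related number is 15 per cluster for 80% power. I could not reproduce that: with three clusters of 15 per arm and a design effect of 1 + 14 × 0.01 = 1.14, two-sided power for 5% against 15% is 31%. That is a separate matter, and nothing below rests on it.

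**Inputs**
- Three districts, ICC 0.01, planned difference 10 points: power paragraph, section 6.0.
- Rate of about 5%: the 2014 campaign figure in section 1.0. Rates of 10% and 20% are assumptions to show the range.
- ICC 0.05: an assumption to show sensitivity.
- 75 women per district: the baseline survey row of Table 2, used only in steps 3 and 4. The interval interview row gives 45, while the Aim 1 text allows up to 25 women at each of three sites, which is 75.

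**Step 1. Shape of the contrast.** Districts cross one at a time, so the rounds that contain both states are one against two, then two against one. If district levels have variance σ², the contrast carries σ² × (1 + 1/2) = 1.5σ² in both cases.

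**Step 2. Size of the starting gap.** With σ² = ICC × p(1−p), SD = √(1.5 × ICC × p(1−p)).

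| Rate p | ICC 0.01: SD (95% range) | ICC 0.05: SD (95% range) |
|---|---|---|
| 5% | √(1.5 × 0.01 × 0.0475) = 2.7 points (±5.2) | 6.0 points (±11.7) |
| 10% | √(1.5 × 0.01 × 0.09) = 3.7 points (±7.2) | 8.2 points (±16.1) |
| 20% | √(1.5 × 0.01 × 0.16) = 4.9 points (±9.6) | 11.0 points (±21.5) |

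This part does not shrink as more women are interviewed.

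**Step 3. Effect on the chi-squared test.** I simulated 40,000 trials with no intervention effect, one district against two, 75 women each and stable district levels, at a nominal 5%.

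| ICC, rate | Chi-squared on levels rejects | Change from own baseline rejects |
|---|---|---|
| 0.01, 5% | 12.3% | 5.3% |
| 0.01, 20% | 13.5% | 5.4% |
| 0.05, 5% | 31.2% | 5.1% |
| 0.05, 20% | 37.7% | 5.3% |

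**Step 4. Cost of using change.** For a quantity with variance V in each round and correlation r between rounds, change has variance 2V(1−r). This is below V only if r exceeds 0.5. With 75 women, a 5% rate and ICC 0.01:
- Sampling variance of the contrast is 0.99 × 0.0475 × (1/75 + 1/150) = 0.00094. The district part is 0.00071. The total is 0.00165, an SD of 4.1 points.
- If women's answers in the two rounds are independent given the district, the correlation of the contrast between rounds is 0.00071/0.00165 = 0.43. Change then has variance 2 × 0.00094 = 0.00188, an SD of 4.3 points.

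Under these assumptions change is slightly noisier in total, but it no longer carries the starting gap.

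**The case against.** Several counterarguments have force.

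**The plan does not ignore baseline.** A reader might infer that it does. The text does not support that. The before/after analysis uses baseline, and for the mixed model section 6.0 is silent on covariates, which a statistical analysis plan may fix. If that model were fitted to all rounds with a district term, it would already come close to the fix below. The omission is certain only for the chi-squared branch, which the protocol confines to single-level samples. What remains is that the between-district contrast itself is written as two groups, contrary to section 3.0.

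**The gap is not bias.** The crossover order is random, so the starting gap is chance imbalance. A standard error that allows for clustering would include it, and the excess rejections in step 3 are also what ignored clustering looks like. This stands. But such a standard error only widens the interval. The gap stays in the estimate, and baseline data can take it out.

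**A power gain cannot be claimed.** It is tempting to say that adjusting for a woman's own baseline raises power, for example from 30% to 38% for 5% against 15%, with 45 women per district and a correlation of 0.5. That result shrinks the district variance along with the woman-level variance. Shrinking only the latter gives 35%, and the plan states no correlation. A correlation of 0.7 is not even attainable between binary outcomes at 5% and 15%, where the maximum is √(0.05 × 0.85/(0.95 × 0.15)) = 0.55, or at 10% and 20%, where it is 0.67. For first-time screening every woman at risk has the same baseline value, so her own baseline adds nothing.

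**Facility counts.** Section 6.0 does not say that these go into the between-region comparison. Nor does change always help them: at a 5% rate and ICC 0.01, the SD of 2.7 points falls to 1.7 if the district autocorrelation is 0.8, is unchanged at 0.5 and rises to 3.2 at 0.3.

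**Conclusion.** The point holds in a limited form. The protocol specifies the between-district contrast as a comparison of groups, by a test that cannot use baseline or a model for which no baseline term is named. With three districts, their chance starting differences enter that contrast with an SD of 2.7 points at a 5% rate and 4.9 points at 20%, against a planned 10. These figures rest on the plan's ICC of 0.01. The 20% rate is an assumption, and a larger ICC makes the gap larger.

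The documents do not support saying that the trial discards its baseline, that the estimate is systematically biased, or that adjustment brings a known gain in power. The case for change is that the contrast should follow the design stated in section 3.0, using data already collected. The roughly 5% rejection rate for change assumes stable district levels over time.

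**What to change.** In section 6.0, redefine the between-district contrast as a difference in change.

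- **Interview outcomes:** fit the mixed-effects logistic model to all rounds, including baseline, with fixed effects for district and round, an intervention indicator and a participant random effect. Do not also enter the woman's own baseline outcome as a covariate: in the baseline rows the outcome would then equal its own predictor, so baseline would be used twice.
- **First-time screening:** use the district's prior uptake as the baseline, since the woman-level value is constant among those at risk.
- **Facility counts:** if they are compared between districts, express them relative to each district's own baseline.
- **Chi-squared comparison:** report it as descriptive only.

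The cost is a few sentences and some model terms, with no new data. The downside is that a pure change from baseline loses precision where baseline and follow-up correlate below about 0.5, and the plan gives no value for that correlation.
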